## **Vernakalant IV Sterile Concentrate Prospective Safety Registry Study**

Sponsor Protocol Identifier: 6621-049-00

3 August 2016

---

be made to enrol sites that can recruit an adequate number of AF patients during the study enrolment period. Regional variation within countries may also be considered in site selection.

### **6.3.2 Patient Enrolment**

Patients who meet all the inclusion criteria and none of the exclusion criteria may be included in the PASS. Patients will be selected for enrolment in the PASS after the decision has been made to administer vernakalant IV. PASS participation will not influence their course of treatment in any way.

Sites will be required to maintain a screening log of eligible patients, including their gender and age. The log will document all patients that may be included or excluded from the PASS, in order to assess the potential study population. To the extent possible, consecutive eligible patients will be included and reasons for non-participation will be documented.

### **6.4 Patient Withdrawal**

Patients may withdraw consent at any time. If a patient is withdrawn prior to completing the PASS follow-up period, the reason for withdrawal is to be documented. All information already collected as part of the study will be retained for analysis unless the patient requests otherwise.

## **7 DATA COLLECTION**

### **7.1 Collection of Required Data Elements**

Scheduled assessments for the study are presented in the Registry Assessment Flow Chart provided in this section. All data elements will be collected from information routinely recorded in the medical record, or will be prospectively recorded by the investigator for the purposes of the study.

Data will be collected via an electronic case report form (eCRF). Data describing vernakalant IV administration and dosing at baseline, and observations during study follow-up (from start of first infusion through the 24-hour period following last infusion of vernakalant IV or discharge/end of medical encounter, whichever is earlier) will be collected; site personnel will enter (or transfer if collected on a paper case report form) the collected data in the appropriate eCRFs. Information on concomitant medications and administration of other therapies to restore/maintain sinus rhythm during the index hospitalization for stays exceeding 24 hours following last infusion of vernakalant IV will be collected, up to a maximum of 7 days following last infusion of vernakalant IV. For prospectively recorded data elements, expected to include NYHA class [Ref. 5.4: 443] and elements of medical history at presentation which may not be available in the medical record, the investigator will record the data in the eCRF and add any

## **Vernakalant IV Sterile Concentrate Prospective Safety Registry Study**

Sponsor Protocol Identifier: 6621-049-00

3 August 2016

---

source documentation (described further in Section 11.2) such as paper worksheets, or printed ECG tracings to the medical record. Baseline ECG tracings recorded as part of standard of care during the index hospitalization and prior to vernakalant administration and ECGs corresponding to arrhythmic HOIs and SAEs during the follow-up period may also be requested.

No follow-up visits or examinations, laboratory tests, or procedures are mandated as part of this study.

### **7.1.1 Description of Key Data Elements**

The list of key data elements to be collected is described below.

The main data elements that will be collected as part of the registry protocol will include:

- **Patient demographics** (date of birth or age, gender, race, body weight [kg], BMI)
- **Hospital admission/medical encounter in which Vernakalant IV was administered**
  - Setting (intensive care unit [ICU], coronary care unit [CCU], surgical unit, medical ward, emergency department [ED])
  - Date/time of admission and discharge
  - Primary complaint (reason for admission)
  - Medical condition for which vernakalant IV is prescribed (indication for use)
- **Characterisation of AF episode for which Vernakalant IV was administered**
  - AF type (surgery vs. non-surgery)
  - Duration of current AF episode (hours), date of onset
  - AF symptoms at presentation
- **Presenting medical conditions**
  - NYHA heart failure class [Ref. 5.4: 443]
    - Class I. Patients with cardiac disease but without resulting limitation of physical activity. Ordinary physical activity does not cause undue fatigue, palpitation, dyspnea, or anginal pain.
    - Class II. Patients with cardiac disease resulting in slight limitation of physical activity. They are comfortable at rest. Ordinary physical activity results in fatigue, palpitation, dyspnea, or anginal pain.
    - Class III. Patients with cardiac disease resulting in marked limitation of physical activity. They are comfortable at rest. Less than ordinary activity causes fatigue, palpitation, dyspnea, or anginal pain.
    - Class IV. Patients with cardiac disease resulting in inability to carry on any physical activity without discomfort. Symptoms of heart failure or the anginal

## Vernakalant IV Sterile Concentrate Prospective Safety Registry Study

Sponsor Protocol Identifier: 6621-049-00

3 August 2016

---

syndrome may be present even at rest. If any physical activity is undertaken, discomfort is increased.

- Myocardial infarction (MI) or acute coronary syndrome (ACS) within 30 days
- Haemodynamic stability
- Systolic/diastolic blood pressure
- Heart rate
- Severe aortic stenosis
- Severe bradycardia (without pacemaker)
- Sinus node dysfunction
- Heart block (2nd or 3rd degree)
- Left atrial clot (if known) - for those receiving routine echocardiogram
- Left ventricular hypertrophy (size of the left atrium), thickness of septum, left ventricular ejection fraction (if ascertained as part of usual care)
- Baseline electrocardiogram (rhythm, ventricular rate, QRS duration, QT interval)
- Hepatic impairment as determined by results of liver function testing performed as part of usual care

- **Concomitant Medications:** All prescription and non-prescription medications taken within 24 hours prior to, and during, the index hospitalisation, including (but not limited to)
  - Rate control
  - Rhythm control
  - Blood pressure regulation
  - Anti-thrombotics
  - Anti-coagulants
  - Hypercholesterolemia / hyperlipidemia

Information on concomitant medications administered during the index hospitalisation for stays exceeding 24 hours following last infusion of vernakalant IV will be collected, up to a maximum of 7 days following last vernakalant infusion.

- **Selected blood chemistries** (with lab reference ranges) collected as part of usual care, including, but not limited to:
  - Serum potassium
  - Magnesium
  - Troponin
  - Creatinine

**Vernakalant IV Sterile Concentrate Prospective Safety Registry Study**

Sponsor Protocol Identifier: 6621-049-00

3 August 2016

---

- Liver function tests and other analytes (e.g., platelets) required for estimation of liver function using established algorithms
- **Medical history**
  - History of heart failure (year of diagnosis)
    - Prior hospitalisations for acute heart failure (most recent, number in last 6 months)
    - Previously documented left ventricular ejection fraction (most recent)
  - History of AF
    - Year of initial diagnosis
    - Classification (first onset, paroxysmal, persistent, permanent, post-operative, Wolff-Parkinson-White, other?)
  - Pacemaker (yes/no, year implanted)
  - Implantable cardioverter defibrillator (ICD) (yes/no, year implanted)
  - History of cardiovascular disease
    - Valvular heart disease
    - Clinically meaningful valvular stenosis
    - Hypertrophic obstructive myopathy
    - Restrictive cardiomyopathy
    - Constrictive pericarditis
    - MI, angina, stroke, ACS, vascular surgery (stent, coronary artery bypass graft, etc.)
    - Hypertension
  - **Other medical and lifestyle history**
    - Diabetes
    - Smoking
    - Hyperlipidemia/ hypercholesterolemia
- **Dosing/Administration of vernakalant IV**
  - Total number of infusions during treatment episode
  - Total dose with each infusion
  - Start/stop times for each infusion
  - Amount of time between each infusion
  - Time to successful conversion
- **Methods of site monitoring of patients during and following each vernakalant infusion per SmPC guidance**

## **Vernakalant IV Sterile Concentrate Prospective Safety Registry Study**

Sponsor Protocol Identifier: 6621-049-00

3 August 2016

---

- Duration and frequency of blood pressure measurements during each infusion, during 15 minute post-infusion and up to two hours post-infusion, and type of healthcare provider performing such monitoring
- Type and duration of cardiac rhythm monitoring during and up to two hours post-infusion, and type of healthcare provider performing such monitoring
- **Administration of other therapies for restoration/maintenance of sinus rhythm during the index hospitalisation or medical encounter**
  - IV and oral rhythm control pharmacologic agents (drug class, administration time relative to any infusion of Vernakalant IV)
  - Electrical cardioversion (type [external, transvenous, or transesophageal] and administration time relative to any infusion of vernakalant IV)
  - Maze ablation pacemaker or ICD implantation or any other surgical procedures to restore sinus rhythm
- Information on other therapies to restore/maintain sinus rhythm administered during the index hospitalization for stays exceeding 24 hours following last infusion of vernakalant IV will be collected, up to a maximum of 7 days following last infusion of vernakalant IV
- **Pre-specified medically significant HOIs**
  - Significant hypotension (symptomatic hypotension with systolic BP <90 mmHg, requiring treatment with vasopressors)
  - Sustained ventricular tachycardia (VT) with a ventricular heart rate > 120 beats per minute with duration > 30 seconds or VT that required intervention with either electrical shock or anti-arrhythmic drugs, or
  - Torsade de Pointes with a duration of >10 seconds
  - Ventricular fibrillation of any duration
  - Significant atrial flutter defined as: atrial flutter with 1:1 atrioventricular conduction of >10 seconds duration and ventricular rate >200 bpm
  - Significant bradycardia defined as: bradycardia requiring electrical pacing (temporary or permanent) or any other serious adverse event reports involving bradycardia
- **Risk minimization materials**

Collection of data regarding use of risk minimization materials began in August 2014.

- Use of Pre-Infusion Checklist by HCP
- Health Care Provider/Appropriate Use of Brinavess™ card
  - Receipt and date of receipt by site
  - Read by HCP

**Vernakalant IV Sterile Concentrate Prospective Safety Registry Study**

Sponsor Protocol Identifier: 6621-049-00

3 August 2016

### 7.1.2 Schedule of Assessments

**Follow-up from start of first infusion through earlier of 24 hours after last infusion or hospital discharge/end of medical encounter)**

Assessment	Source	Baseline	Follow-up from start of first infusion through earlier of 24 hours after last infusion or until discharge/end of medical encounter
Informed consent/assent obtained (may be prior to or following administration of vernakalant IV, see further detail in Section 12.1)	Patient unless incapacitated, may seek proxy consent or waiver of consent based on EC approval	X	
Inclusion/exclusion criteria	Site staff	X	
Patient demographics (date of birth or age, gender, race, body weight, BMI)	Medical record or supplemental collection	X	
Hospital admission/medical encounter in which vernakalant IV was administered (setting, date/time of admission and discharge, primary complaint/reason for admission)	Medical record	X	
Characterisation of atrial fibrillation episode for which vernakalant IV was administered (surgery or non-surgery setting, onset of current episode)	Medical record	X	
Presenting medical conditions (NYHA class, myocardial infarction, acute coronary syndrome, haemodynamic stability, systolic/diastolic blood pressure, severe aortic stenosis, severe bradycardia, sinus node dysfunction, 2 nd or 3 rd degree heart block, baseline electrocardiogram, left ventricular ejection fraction, hepatic impairment)	Medical record or supplemental collection- NYHA class is anticipated to require supplemental collection	X	

**Vernakalant IV Sterile Concentrate Prospective Safety Registry Study**

Sponsor Protocol Identifier: 6621-049-00

3 August 2016

Concomitant Medications: prescription and non-prescription medications taken within 24 hours prior to, and during, the index hospitalization* (to include, but not limited to, cardiovascular medications such as rate control, rhythm control, blood pressure regulation, anti-thrombosis, hypercholesterolemia)	Medical record	X	X*
Standard of care blood chemistry (e.g. serum potassium, magnesium, troponin, creatinine, liver function tests)	Medical record	X	
History of heart failure (year of diagnosis, recent hospitalisations, left ventricular ejection fraction within last year, current medications)	Medical record or supplemental collection	X	
History of atrial fibrillation (year of initial diagnosis, classification: first onset, paroxysmal, persistent, permanent, post-operative, Wolff-Parkinson-White or other)	Medical record or supplemental collection	X	
Pacemaker (yes/no, year implanted)	Medical record or supplemental collection	X	
Implantable cardioverter defibrillator (ICD) (yes/no, year implanted)	Medical record or supplemental collection	X	
History of cardiovascular disease (valvular heart disease, clinically meaningful valvular stenosis, hypertrophic obstructive myopathy, restrictive cardiopathy, constrictive pericarditis, myocardial infarction, angina, stroke, acute coronary syndrome, vascular surgery, hypertension)	Medical record or supplemental collection	X	
Other medical and lifestyle history (diabetes, smoking, hyperlipidemia)	Medical record	X	

**Vernakalant IV Sterile Concentrate Prospective Safety Registry Study**

Sponsor Protocol Identifier: 6621-049-00

3 August 2016

Dosing/Administration of Vernakalant IV (total number of infusions, total dose with each infusion, start/stop time for each infusion, amount of time between each infusion, time to successful conversion, and methods of site monitoring of patients during and following vernakalant infusion per SmPC guidance)	Medical record	X	X
Administration of therapies for restoration/maintenance of sinus rhythm during the index hospitalisation* (IV and oral rhythm control pharmacologic agents, electrical cardioversion, Maze ablation, pacemaker or ICD implantation or any other surgical procedure to restore sinus rhythm, start/stop time for IV or electrical treatments)	Medical record	X	X*
Mandatory reporting of pre-specified medically significant HOIs (see section 8 for definitions and reporting requirements)	Investigator/Site staff	X	X
Mandatory reporting of SAEs (see section 8 for definitions and reporting requirements)	Investigator/Site staff	X	X

\*Data on concomitant medications and therapies (oral, IV meds, electrical cardioversion, and/or surgical procedures) for restoration/maintenance of sinus rhythm during the index hospitalization for stays exceeding 24 hours following last infusion of vernakalant IV will be recorded up to 7 days following the last vernakalant IV infusion.

## 7.2 Collection of Data Retrospectively

To minimize further delay to completion of the study, data will be collected retrospectively from patients who have received Brinavess™ but were not enrolled in the study. To reflect today's real world setting, retrospective data will only be collected from patients who received Brinavess™ after the additional risk minimization measures were implemented in April 2013. This would mean that data from patients would be included both retrospectively and prospectively at all new and existing sites.

The inclusion of these retrospective data from patients already treated with Brinavess™ would allow the primary objective study to be met fully, whilst facilitating the timely completion of this trial.

**Vernakalant IV Sterile Concentrate Prospective Safety Registry Study**

Sponsor Protocol Identifier: 6621-049-00

3 August 2016

---

At the completion of the study, stratified analyses will be used to present the results. Full statistical methods and analyses will be described in the Statistical Analysis Plan (SAP).

Patients are consecutively enrolled into SPECTRUM based on when they present at the participating site. In order to minimize any potential selection bias at the patient level, retrospective data collection will be conducted to include all patients already treated with BrinavessTM but not enrolled in SPECTRUM, at existing and newly qualified sites, with available key data. Specifically, data will be included from all patients who;

1. Have received BrinavessTM since April 2013 but were not enrolled in SPECTRUM.
2. Have available in their hospital records the key data variables as stipulated in section 7.2.1.
3. Provide their informed consent or the site obtains a waiver from their IEC.

Both retrospectively and prospectively included patients have to fulfill the same inclusion and exclusion criteria. As neither group of patients are selected randomly, this approach is not expected to yield selection bias. In addition, results will be reported overall and stratified by method of enrollment. As those who refuse to consent to participate, will not have provided their consent to use their data it would not be possible to compare baseline characteristics of those who refuse vs those who participate. To ensure the overall sample is not dominated by any one site or country by the inclusion of retrospective data, any site or country who reaches their limit based on the inclusion of retrospective data will be closed and the resources used to open other sites/countries. Enrolment will be capped at 10% per site (200 patients) and 40% per country (800 patients). This cap includes collection of patient data both prospectively and retrospectively.

The limitations for enrolling patients prospectively include lack of available staff to discuss the study with the patient and ask for their consent, (this typically happens over the weekend, after hours, when the Investigator is on vacation or off duty for other reasons) and patients unwilling to give their consent to use their data. For retrospectively enrolled patients the limitations are the same. Some sites may not have sufficient staff to contact patients treated previously and again, the patient may be unwilling to give their consent to use their data.

As stated above both retrospectively and prospectively included patients will have to fulfill the same inclusion and exclusion criteria, neither group of patients would be selected randomly, thus this approach is not expected to yield selection bias. In addition, results will be reported overall and stratified by method of enrollment.

SPECTRUM is an observational study that does not use randomization to select the sample. Treated patients are sequentially enrolled, based on provision of informed consent. Inclusion of patients retrospectively will also not use randomization as the goal is to enroll all patients, at the selected sites, who were treated with Brinavess and provided their informed consent. This will ensure that patients

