## **Vernakalant IV Sterile Concentrate Prospective Safety Registry Study**

Sponsor Protocol Identifier: 6621-049-00

3 August 2016

---

selected retrospectively and prospectively are selected in the same manner. This will minimize the risk of any potential selection bias.

Missing data is always a concern; and including patients retrospectively could increase the amount of missing data. However the impact of missing data on the evaluation of the HOIs and other rare events is not anticipated to be a concern as this information is routinely collected in the patient's hospital record. Therefore these event rates at the completion of the study would not be biased downward. Further, any possible observer bias by selecting patients retrospectively will be minimised by only including patients with the key data variables as stipulated in section 7.2.1 and the assessment of whether an event is characterized as an HOI is adjudicated by an independent Safety Review Committee (SRC).

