### **Informed consent**

Patients who fulfil the criteria above will be contacted either at clinic during their next routine follow up cardiology appointment, or by phone and / or mail. The approved informed consent form will then be discussed in detail with the patient and if they agree to take part, the patient will personally sign and date the consent form.

If local regulations permit, sites may also ask their IEC for an informed consent waiver.

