### **Identification of retrospective patients**

As soon as local regulatory and Ethics Committee approval are obtained (where applicable) sites will be able to enrol retrospective patients concurrently with prospective patients.

Strategies for identifying retrospective patients will vary between sites as a result of varying staff availability and record keeping. Sites with searchable electronic patient records for example will find it easier to identify patients than sites without.

Several methods will be employed to identify retrospective patients who have been treated with Brinavess since April 2013.

1. Patients will be approached at their routine clinic visit. If a study team member notices during this visit that Brinavess treatment has been previously given, the study will be discussed with the patient at this time and asked if they are willing to give their consent to take part.
2. Following a search of the hospital records,
  - a. Identified patients will receive a telephone call, the study discussed with them and at their next routine visit asked if they are willing to give their consent to take part. OR
  - b. Identified patients will receive a telephone call, the study discussed with them, information mailed to the patient and then the patient will be asked to sign and mail back the completed consent form. OR

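### The claim that adding retrospective patients brings no selection bias is unsupported: without a usable consent waiver, patients who died cannot enter that stratum, so pooled fatal event rates can be understated by up to about 22%

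*Protocol*

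**What the plan says.** Protocol 7.2 extends data collection to patients treated since April 2013 who were not enrolled at the time. On the ground that neither group is chosen at random, it says that "this approach is not expected to yield selection bias". It repeats the argument and adds that the two groups are chosen in the same way.

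A retrospective patient must meet this condition: "Provide their informed consent or the site obtains a waiver from their IEC". Under the consent route, patients "will be contacted either at clinic during their next routine follow up cardiology appointment, or by phone and / or mail", and after discussion "the patient will personally sign and date the consent form". The first identification method listed is "Patients will be approached at their routine clinic visit". The others are a telephone call or a letter after a records search, with consent given at a visit or by post. The waiver is optional: "If local regulations permit, sites may also ask their IEC for an informed consent waiver".

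The same section discusses missing data, argues that HOIs are routinely in the hospital record, and concludes: "Therefore these event rates at the completion of the study would not be biased downward".

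Protocol 10.1 takes as its analysis population all enrolled patients documented as having received the drug. SAP 4.2 and 5.1.1 are narrower. They require a signed consent form and do not mention waivers.

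**The concern.** Non-random selection gives no protection against selection bias, and shared eligibility criteria do not prevent selection on the outcome. What matters is whether having an event changes the chance of being included.

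For retrospective patients, inclusion is decided after the outcome is known. A patient treated in April 2013 would be approached about 40 months later at the date of this protocol (August 2016), and about 45 months later at the planned Finnish start (January 2017). A patient who died in between cannot sign.

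The study exists to estimate rare, serious events, some of them fatal. SAP Tables 16.1b.1 and 16.1b.3 tabulate SAEs by fatality for the pooled and retrospective sets. If no waiver is usable, the fatal column of the retrospective table is empty by construction, and the pooled table divides by a denominator that includes a stratum in which a fatal event could not be seen. A reader of the final report would have no sign of this. The reasons for non-participation listed in SAP 5.1.1 are no consent, not approached before administration, and recent participation in an investigational trial. Death and failure to make contact are not among them.

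**Working it through.** **Inputs.** Target N = 2,000 and expected incidence of 0% to 0.22% per HOI (Protocol 10.7, SAP 4.1). Planned retrospective patients = 435, of whom 345 are Finnish (Protocol Appendix I). Interval method: two-sided 95% Clopper-Pearson (same sections). The documents give no inclusion probabilities, so those below are assumptions.

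**The plan's own figure.** The worked example has expected proportion 0.003 and N = 1,500, so x = 4.5. Beta quantiles give 0.0009 to 0.0073, which matches the stated 0.001 and 0.007. All 44 pairs of limits in Table 1 match to three decimals.

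**Exposed share.** w = 435/2,000 = 21.75%.

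**Fatal events, no usable waiver.** Let f be the true fatal incidence, equal in both strata. The retrospective stratum shows 0, so the pooled rate is (1 − 0.2175)f = 0.7825f, a relative loss of 21.75%. This is the maximum for fatal events. If fatal HOIs are the only ones lost, the loss in the all-HOI rate is 0.2175 times the fatal share: 2.2% if 10% of HOIs are fatal, 10.9% if 50% are.

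**HOIs in general.** Let r be the inclusion probability of a patient with an HOI relative to one without, in the retrospective stratum only. Then p_retro = rp/(rp + 1 − p) and pooled = w·p_retro + (1 − w)p. The relative bias is close to −0.2175(1 − r). At p = 0.22%:

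| r (assumed) | pooled rate | relative change |
|---|---|---|
| 0 | 0.172% | −21.8% |
| 0.5 | 0.196% | −10.9% |
| 0.75 | 0.208% | −5.4% |
| 0.9 | 0.215% | −2.2% |
| 1 | 0.220% | 0 |
| 1.25 | 0.232% | +5.4% |

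For r = 0.5: p_retro = 0.0011/(0.0011 + 0.9978) = 0.110%, and pooled = 0.2175 × 0.110% + 0.7825 × 0.220% = 0.196%.

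**Precision if the prospective stratum is read alone.** Planned N = 2,000 − 435 = 1,565. At 0.22% the interval is 0.05% to 0.60%, against 0.07% to 0.54% at N = 2,000. With zero events the upper limit, 1 − 0.025^(1/N), is 0.24% against 0.18%.

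**The case against.** The case on the other side has real weight.

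- **Other entry routes exist.** Consent by post means that continued follow-up at the site is not required. Protocol 6.1 and 12.1 allow a guardian or legal representative, so an incapacitated patient is not necessarily shut out, although 7.2 speaks of a personal signature. A waiver could admit patients who died. If every Finnish site obtained one and those patients were analysed, the exposed share would fall to 90/2,000 = 4.5%. This stands, but the waiver is optional, the documents do not say which sites have one, and the SAP definition read literally drops the patients it would rescue.
- **Results by enrolment method are already planned.** Protocol 7.2 and 10.2 and SAP 5 and 5.4 all provide them, so the prospective HOI tables need no new analysis. This stands. The adjusted estimate in Protocol 10.2 does not help, because adjusting for enrolment method cannot restore patients who were never included, and the SAP does not describe that estimate.
- **The direction is not known for survivable events.** Patients with treated hypotension or a paced bradycardia may have more cardiology visits and be easier to find. This stands.
- **The shifts are small.** At 0.22% they lie inside the N = 2,000 interval. This stands, but that interval reflects sampling error only.
- **The prospective stratum has its own problems.** Protocol 7.1.2 lets consent follow dosing, and 7.2 admits that weekend and after-hours patients are missed. Retrospective collection is meant to recover patients of that kind, and Protocol 7.2 counts on it to meet the primary objective. This stands, and it argues against simply demoting the pooled estimate.

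**Conclusion.** The no-selection-bias statements in Protocol 7.2 are unsupported. Where no waiver is obtained, or where the SAP's signed-form requirement is applied literally, patients who died are lost from the retrospective stratum. Pooled fatal HOI and SAE incidence can then be understated by up to 21.75%. That figure assumes the Appendix I split is achieved, the true fatal rate is the same in both strata, and no deceased patient enters through a waiver. For non-fatal HOIs the size and sign depend on an inclusion ratio that the documents do not give.

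Two stronger readings are tempting and should not be drawn. A reader might infer that the pooled rate is the designated primary estimate. Neither document says so: in Protocol 10.2 and SAP 5.4 the word primary attaches to the 0-2 hour window, and no lead estimate is named among the overall, prospective and retrospective tables. A reader might also infer that the HOI rates are shown to be biased downward, and that the protocol's sentence denying this is false. That sentence closes an argument about missing data in the record. It leaves the question of who is included unaddressed, and for survivable HOIs a downward bias is not established.

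**What to change.** 1. **Protocol 7.2:** withdraw the statements that selection bias is not expected and that the two groups are chosen alike. Say that the assurance about downward bias covers missing data only.
2. **SAP 4.2 and 5.1.1:** amend the analysis-set definition so that patients entered under an ethics committee waiver are included, in line with Protocol 7.2 and 10.1.
3. **Screening log (Protocol 6.3.2), SAP Figure 1 and Table 4.2:** state that they cover every identified retrospective candidate treated since April 2013. Record age, sex and the reason for non-inclusion (died, unreachable, declined, key data missing), as far as local rules permit. Report the number entered under a waiver. Protocol 7.2 says refusers' baseline characteristics cannot be compared, but the log already provides for age and sex.
4. **SAP 5.4:** present the prospective HOI tables (8.1.2, 8.2.2, 8.3.2) beside the pooled tables as co-lead estimates. Interpret the pooled and retrospective rates with this limitation, and add a sensitivity range over the relative inclusion probability, covering values below and above 1.

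The cost is wording in both documents, extra log entries, and a less favourable statement about the pooled rate. If readers rely on the prospective estimate, the zero-event upper limit is about 0.24% instead of 0.18%. The pooled result on the full sample is still shown.
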